2.3. Benefit/Risk Assessment	Added sub-section headers.	For clarity.
2.3.1. Risk Assessment	In first paragraph, added text for the effect of LY3526318 on other drugs.	Clarification of the potential of LY3526318 exposure to affect metabolism of other drugs.
2.3.1. Risk Assessment	Updated first bullet to specify CYP3A4, plus minor editorial changes.	For clarity.
2.3.1. Risk Assessment	Added a bullet for CYP3A4 and p-glycoprotein (P-gp) substrates.	Based on in vitro data suggesting a potential for PK interactions.
5.1. Study Population	Updated numbers for inclusion and exclusion criteria.	To align with master protocol and ISA numbering system.
	Updated criterion #2051 to specify drugs taken orally or intravenously.	Topical drugs are allowed.
	Added exclusion criterion #2054 for participants that are taking drugs that are sensitive CYP3A4 substrates with a narrow therapeutic index.	Based on in vitro data suggesting potential CYP3A4 inhibition at the proposed LY3526318 dose.
	Added exclusion criterion #2055 for participants that are taking simvastatin at doses greater than 20 mg/day.	Simvastatin is a sensitive CYP3A4 substrate, with a projected maximal increase in exposure <2-fold in combination with LY3526318. Therefore, doses of 20 mg or less are considered safe.
	Added exclusion criterion #2056 for participants that are taking metformin at doses greater than 1000 mg/day.	Based on limited data related to inhibition of renal transporters.
	Added exclusion criterion #2057 for participants that are taking digoxin.	Based on in vitro data suggesting a potential for LY3526318 to inhibit P-gp.
6.6. Concomitant Therapy	Under Potential Drug-Drug Interactions with LY3526318, added reference to Section 5.2 for concomitant medication restrictions.	Reference to added exclusion criteria.

Section # and Name	Description of Change	Brief Rationale
10.3. Appendix 3: List of Excluded Concomitant Medications	Added reference to Section 5.2 and the Manual of Operations for additional information.	Additional information for excluded concomitant medications are listed in Section 5.2 and the Manual of Operations.
Throughout the protocol	Minor editorial and format changes.	Minor, therefore not described.

Table of Contents

1.	Protocol Summary	7
1.1.	Synopsis	7
1.2.	Schema.....	9
1.3.	Schedule of Activities (SoA)	10
2.	Introduction	12
2.1.	Study Rationale	12
2.2.	Background	12
2.3.	Benefit/Risk Assessment	15
2.3.1.	Risk Assessment.....	15

1.1. Synopsis

Protocol Title:

Randomized, placebo-controlled, Phase 2 clinical trial to evaluate LY3526318 for the treatment of chronic low back pain

Rationale:

The purpose of this study is to test whether LY3526318 is efficacious in relieving chronic low back pain (CLBP). LY3526318 is a small molecule that inhibits transient receptor protein ankyrin 1 (TRPA1), a calcium permeable nonselective cation channel that is known to be involved in pain and inflammation.

Data will be collected to assess the safety, and tolerability of LY3526318 in this study population. Pharmacokinetic (PK) properties will also be explored. The totality of data from this proof-of-concept study will assess the benefits and risks associated with LY3526318 and inform decisions for the clinical development of LY3526318.

Objectives and Endpoints:

The primary and secondary objectives and endpoints are stated in the Master Protocol H0P-MC-CPMP (CPMP) and CLBP disease-state appendix (DSA; H0P-MC-CPMP[2]).

Overall Design

This is an 8-week, Phase 2, randomized, double-blind, placebo-controlled study that will compare LY3526318 versus placebo in participants with CLBP.

Disclosure Statement:

This is a randomized, investigator- and participant-blind, placebo-controlled, Phase 2 clinical trial.

Number of Participants:

Approximately 150 participants will be randomly assigned to study intervention **CCI** with the assumption that 15% of the participants will drop out prior to the end of the double-blind treatment period.

Intervention Groups and Duration:

This study includes an 8-week double-blind treatment period.

[figure not shown]
Intervention Name	LY3526318	Placebo
Dosage Level(s)	CCI	Not applicable
Route of Administration and duration	PO	PO

Abbreviations: PO = by mouth; QD = once daily.

Data Monitoring Committee: Yes

Safety reviews are covered by the Assessment Committee charter for the Chronic Pain Master Protocol.

1.2. Schema

Abbreviations: PDEP = preliminary data entry period; V = visit.

*Medication washout and PDEP begins.

**Randomization to either LY3526318 or placebo.

1.3. Schedule of Activities (SoA)

This SoA shows visits and procedures unique to the intervention-specific appendix (ISA) H0P-MC-BP02 (BP02) for LY3526318. Please refer to the CPMP Master Protocol and the CLBP DSA H0P-MC-CPMP(2) SoAs for additional information.

	Randomization to ISA	Double-Blind Treatment				Early Discontinuation	Notes
	V3	V4	V5	V6	V7	ED	
Study Week	0	2	4	6	8		
Visit Window (days)		±3					
Physical examination	X		X		X	X	Symptom-directed physical exam (see Section 8.2.1) at V5, V7, and ED (if applicable).
Vital signs	X	X	X	X	X	X	At V3, vitals should be taken predose and at approximately 2 and 4 hours post dosing. At V4, V5, V6, and V7, vitals should be taken predose. Pulse rate, respiratory rate, blood pressure, and temperature taken with participant in a sitting position.
ECG			X		X	X	Single ECGs at V5, V7, and ED (if applicable).
Study intervention	X	X	X	X	X		See Section 6.1.
Intervention compliance		X	X	X	X	X	
Clinical Laboratory Tests and Sample Collection							
Hematology		X	X	X	X		
Chemistry		X	X	X	X		
Lipid panel		X	X	X	X		
Urinalysis					X		
Urine pregnancy	X	X	X	X	X	X	For all WOCBP at V3: collect sample before dosing.
Urine drug screen	X		X		X	X	See Section 5.3.2.
HbA1c	X				X	X	

	Randomization to ISA	Double-Blind Treatment				Early Discontinuation	Notes
	V3	V4	V5	V6	V7	ED	
Study Week	0	2	4	6	8		
Visit Window (days)	±3						
PK sample	X	X	X	X	X	X	At V3, samples should be taken at 2 and 4 hours (±15 minutes) post dosing. At V4, V5, V6, and V7, a sample for PK should be taken before the dose is administered; participants should be asked to refrain from taking their dose on V4-V7 until they have their clinic visit and after the blood sample is taken. The date and time of LY3526318 administration prior to the PK sampling will be recorded, i.e., the dose administered in the clinic at V3 and the last at-home dose prior to each of V4, V5, V6, and V7.
CCI							
Participant Device							
Participant returns device					X	X	If a dBM device is used, the participant will return the device to the site at V7 or ED (if applicable).

Abbreviations: **CCI**; ECG = electrocardiogram; ED = early discontinuation; HbA1c = hemoglobin A1c; ISA = intervention-specific appendix; PK = pharmacokinetic; V = Visit; WOCBP = women of childbearing potential.

2. Introduction

This intervention-specific appendix (ISA) H0P-MC-BP02 (BP02) is an appendix to the H0P-MC-CPMP (CPMP) Master Protocol and contains unique study elements specific for LY3526318. The master protocol contains the overarching study elements that govern the chronic low back pain (CLBP) disease-state appendix (DSA) CPMP(2) and this ISA BP02.

2.1. Study Rationale

The purpose of this study is to test whether LY3526318 is efficacious in relieving CLBP. Data will be collected to assess the safety and tolerability of LY3526318 in this study population. Pharmacokinetic (PK) properties will also be explored. The totality of data from this proof-of concept (PoC) study will assess the benefits and risks associated with LY3526318 and inform decisions for the clinical development of LY3526318.

2.2. Background

The transient receptor potential (TRP) ion channel family comprises a group of 28 nonselective cation channels that are distinct from classical voltage gated ion channels. Among these, transient receptor potential ankyrin 1 (TRPA1) is a calcium-permeable nonselective cation channel, which is expressed in the axons and in both peripheral and central terminals of nociceptors. It is also considered to be important as a chemosensor of nociception (Koivisto et al. 2018; Maatuf et al. 2019; Wang et al. 2019). TRPA1's involvement in pain and inflammation and its localization in sensory neurons are known (Bodkin and Brain 2011; Ückert et al. 2017). Due to its role in evoking pain and eliciting an aversive response, TRPA1 may be a promising target for treating pain (Benemei et al. 2017; Berta et al. 2017; Demartini et al. 2017; Maatuf et al. 2019; Wang et al. 2019).

LY3526318 is an orally administered, potent, and selective novel antagonist of TRPA1 under development by Lilly.

[figure not shown]
LY3526318 has been evaluated in 2 completed and 1 ongoing Phase 1 clinical studies.

Completed Study	J2D-MC-CVAA (CVAA)
Population	Healthy participants
Study Design	2-part, placebo-controlled, randomized, single and multiple-dose escalation study.
LY3526318 Dose	CCI

Objectives	
Part A: To evaluate safety, tolerability, and PK of LY3526318 in healthy participants following a single oral dose.
 
Part B: To evaluate safety, tolerability, and PK of LY3526318 in healthy participants following multiple once-daily oral doses for 14 days.

-------------------	---

Completed Study	J2D-MC-CVAB (CVAB)
Population	Healthy female participants
Study Design	Randomized, double-blind, placebo-controlled, 4-way crossover study.
LY3526318 Dose	Each participant was randomly assigned to receive 4 unique doses of study drug in a ratio of 3 LY3526318: 1 placebo, in a crossover manner with at least 14 days of washout between doses. CCI
Objectives	To assess target engagement of TRPA1 with cinnamaldehyde (CA)-induced dermal blood flow (DBF) after a single dose of LY3526318.

Ongoing Study	J2D-MC-CVAC (CVAC)
Population	Healthy participants
Study Design	Randomized, double-blind, placebo-controlled, SAD (Part A) and multiple dose (MD; Part B) study.
LY3526318 Dose	CCI
Objectives	
Part A: To evaluate the safety, tolerability, and PK of LY3526318 after a single oral dose administration.
 
Part B: To evaluate the safety, tolerability, and PK of LY3526318 after multiple oral dose administrations.

[figure not shown]

2.3. Benefit/Risk Assessment

Clinical Safety

In Study CVAA, no clinically significant safety or tolerability concerns were identified at the highest single dose administered CCI or the highest multiple dose CCI. Additionally, preliminary data using a new formulation of LY3526318 in Study CVAC showed no clinically significant safety or tolerability concerns at higher exposures following single or multiple doses CCI.

Toxicology Studies and NOEL Exposure

2.3.1. Risk Assessment

Study Intervention

More information about the known and expected risks, SAEs, and reasonably anticipated AEs of LY3526318 may be found in the IB. Information on AEs expected to be related to the investigational product may be found in Section 7 (Reference Safety Information for Assessment of Expectedness of Serious Adverse Reactions) of the IB. Information on SAEs that are expected in the study population independent of drug exposure will be assessed by the sponsor in aggregate, periodically during the course of the study, and may be found in Section 5 (Effects in Humans) of the IB.

2.3.2. Benefit Assessment

Potential benefits for the study participants include

- study-related medical procedures
 - physical examinations
 - laboratory tests
 - electrocardiograms (ECGs)
 - detailed evaluations of low back pain (including X-ray at V1).

As part of Study CPMP, participants to this ISA will report their experience using standard tools that will contribute to the assessment of novel treatments for CLBP. In addition, data collected from this study may also improve our understanding of pathogenesis. Both of which may lead to the development of a new treatment with improved safety and efficacy profile compared to standard of care.

2.3.3. Overall Benefit Risk Conclusion

Taking into account the measures taken to minimize risk to participants participating in this study, the potential risks identified in association with LY3526318 are justified by the anticipated benefits that may be afforded to participants with CLBP.

3. Objectives and Endpoints

The CPMP Master Protocol and CLBP DSA CPMP(2) include objectives and endpoints applicable for this study. This table describes objectives and endpoints specific for LY3526318.

Objectives	Endpoints
Tertiary/Exploratory	
Measure the PK of LY3526318 in participants with CLBP.	Measure of plasma concentrations of LY3526318 to enable PK evaluations.

Abbreviations: CLBP = chronic low back pain; PK = pharmacokinetic.

4. Study Design

4.1. Overall Design

The CPMP Master Protocol describes the overall study design and study design rationale. This section describes visits and overall procedures unique to ISA BP02 for LY3526318 in addition to the procedures outlined in CPMP and CPMP(2).

Double-Blind Treatment Period (Visits 3 through 7)

Each visit is an outpatient visit.

At Visit 3

- participants are randomized to LY3526318 or placebo
- the site completes the BP02 baseline procedures and sample collection
- participants receive their oral study intervention
- the site collects participants vitals at 2 and 4 hours after the completion of the oral administration
- the site completes all post-treatment sample collection and safety monitoring, and
- the site instructs participants to continue with study restrictions and Numeric Rating Scale (NRS) diary entries before their visit discharge.

At Visits 4 through 7

- the site reviews available safety data and completes pre-dose procedures and sample collection
- participants continue oral study intervention
- the site completes all sample collection and safety monitoring noted in the Schedules of Activities (SoAs), and
- the site instructs participants to continue with study restrictions and NRS diary entries before their visit discharge.

4.2. Scientific Rationale for Study Design

The master protocol describes the overall study design rationale.

4.3. Justification for Dose

A large, stylized logo consisting of the letters 'C', 'C', and 'I' in a bright red color. The letters are bold and have a slightly irregular, hand-drawn appearance. They are set against a solid black rectangular background.

4.4. End of Study Definition

A participant is considered to have completed this ISA if he or she has completed all required phases of the study including the last scheduled procedure shown in the ISA SoA.

The end of the study is defined as the date of the last visit of the last participant in the study or last scheduled procedure shown in the ISA SoA for the last participant.

5. Study Population

The CPMP Master Protocol and CLBP CPMP(2) DSA provide eligibility criteria that must be followed for this study. LY3526318-specific inclusion and exclusion criteria are listed here.

5.1. Inclusion Criteria

Participants are eligible to be included in the study only if all of the following criteria apply:

[2050] Are men or women who abide by the reproductive and contraceptive requirements provided in BP02 Section 10.2, Appendix 2.

5.2. Exclusion Criteria

Participants are excluded from the study if any of the following criteria apply:

CCI [REDACTED]

[2052] Have an eGFR of less than 30 ml/min/1.73 m² based on the Chronic Kidney Disease Epidemiology Collaboration (CKD-EPI) formula at Visit 1 or Visit 2.

[2053] Women who are pregnant or breastfeeding.

CCI [REDACTED]

CCI [REDACTED]

CCI [REDACTED]

CCI [REDACTED]

5.3. Lifestyle Considerations

5.3.1. Meals and Dietary Restrictions

Refrain from consumption of Seville oranges, grapefruit or grapefruit juice from 5 days before the start of study intervention until after the final dose.

5.3.2. Substance Use

Positive urine drug screen will not be considered illicit use if the substance is a prescribed concomitant medication for a known pre-existing condition.

5.3.3. Reproductive and Contraception Requirements

Reproductive requirements and contraceptive guidance are provided in Section 10.2, Appendix 2.

6. Study Intervention(s) and Concomitant Therapy

Study intervention is defined as any investigational intervention(s), marketed product(s), placebo, or medical device(s) intended to be administered to/used by a study participant according to the study protocol.

6.1. Study Intervention(s) Administered

The study intervention will be administered orally, CCI [REDACTED]

Intervention Name	LY3526318	Placebo
Dose Formulation	Capsule	Capsule
Unit Dose Strength(s)	CCI [REDACTED]	[REDACTED]
Dosage Level(s)	CCI [REDACTED]	[REDACTED]
Route of Administration	PO	PO
Use	experimental	placebo
IMP and NIMP	IMP	NIMP

Abbreviations: IMP = investigational medicinal product; NA = not applicable; NIMP = noninvestigational medicinal product; PO = by mouth; QD = once daily.

6.2. Preparation, Handling, Storage, and Accountability

The CPMP Master Protocol provides more detail on preparation, handling, storage, and accountability requirements.

6.3. Measures to Minimize Bias: Randomization and Blinding

No additional stratification factors are considered for this ISA.

6.4. Study Intervention Compliance

When participants self-administer study intervention(s) at home, compliance with study intervention will be assessed at each visit. Compliance will be assessed by direct questioning, counting returned capsules, and documented in the source documents and case report form (CRF).

A record of the number of study intervention capsules dispensed to and taken by each participant must be maintained and reconciled with study intervention and compliance records. Intervention start and stop dates, will also be recorded in the CRF.

6.5. Treatment of Overdose

In case of suspected overdose, participants should be monitored for any signs or symptoms of adverse reactions or effects, and supportive care should be provided as necessary. There is no known antidote to LY3526318 therapy.

6.6. Concomitant Therapy

All concomitant therapies that are part of routine care for comorbidities other than chronic pain are allowed and may be used during the study, if it is permitted based on the eligibility criteria. The CPMP Master Protocol provides more detail on concomitant therapy.

A list of medications that are prohibited from Visit 2 to Visit 7 for participants randomized to this ISA study will be provided in the Manual of Operations. Participants may return to their standard of care after Visit 7 is completed, as clinically appropriate.

The logo for CCI (Clinical Care Innovations) is displayed in red text on a black rectangular background. The letters 'C', 'C', and 'I' are bold and sans-serif.

7. Discontinuation of Study Intervention and Participant Discontinuation/Withdrawal

The CPMP Master Protocol and CPMP(2) DSA provides the reasons and procedures for discontinuation of intervention and participant discontinuation that must be followed for this study.

8. Study Assessments and Procedures

Study procedures and their timing are summarized in the CPMP Master Protocol, CLBP CPMP(2) DSA, and ISA BP02 SoAs.

LY3526318-specific assessments and procedures are described here.

8.1. Efficacy Assessments

Planned time points for all efficacy assessments are provided in the SoAs.

8.2. Safety Assessments

Planned time points for all safety assessments are provided in the SoAs.

8.2.1. Physical Examinations

Symptom directed physical examinations of skin, eyes, mouth, lungs, and gastrointestinal tract will be performed at each visit as described in the SoA. Any clinically significant abnormal physical examination findings will be reported as AEs.

8.2.2. Electrocardiograms

Single 12-lead ECG will be obtained as outlined in the SoA using an ECG machine that automatically calculates the heart rate and measures PR, RR, QRS, QT, and QTcF intervals.

8.2.3. Clinical Safety Laboratory Tests

See BP02 Section 10.1 (Appendix 1) for the list of clinical laboratory tests to be performed and to the SoA for the timing and frequency for ISA BP02.

8.3. Adverse Events, Serious Adverse Events, and Product Complaints

See the CPMP Master Protocol for additional details.

8.4. Pharmacokinetics

- Blood samples will be collected for measurement of plasma concentrations of LY3526318 as specified in the SoA.
- A maximum of 3 samples may be collected at additional time points during the study if warranted and agreed upon between the investigator and the sponsor. The timing of sampling may be altered during the course of the study based on newly available data (e.g., to obtain data closer to the time of peak plasma concentrations) to ensure appropriate monitoring.
- Instructions for the collection and handling of biological samples will be provided by the sponsor. The actual date and time (24-hour clock time) of each sample will be recorded.
- The date and time (24-hour clock time) of LY3526318 administration prior to the PK sampling will be recorded i.e. the dose administered in the clinic at Visit 3 and the last at home dose prior to each of Visit 4, Visit 5, Visit 6, and Visit 7.

- Samples will be used to evaluate the PK of LY3526318. Samples collected for analyses of LY3526318 plasma concentrations may also be used to evaluate safety or efficacy aspects related to concerns arising during or after the study.

Drug concentration information that may unblind the study will not be reported to investigative sites or blinded personnel until the study has been unblinded.

8.5. Pharmacodynamics

Pharmacodynamic parameters are not evaluated in this study.

A large, stylized logo consisting of the letters 'C', 'C', and 'I' in a bright red color, set against a solid black rectangular background. The letters are thick and have a slightly irregular, hand-drawn appearance.

9. Statistical Considerations

The CPMP Master Protocol and CLBP DSA CPMP(2) provide statistical considerations. LY3526318-specific considerations are described here.

9.1. Statistical Hypotheses

The CPMP Master Protocol describes the primary hypothesis. CCI

If there is no treatment difference between placebo and LY3526318, the probability of passing the efficacy criterion specified above (i.e., false positive) is less than 0.1. The simulation for the power calculation and sample size determination was carried out using the Fixed and Adaptive Clinical Trial Simulator (FACTS) Version 6.0.

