9.5. Sample Size Determination

Up to approximately 150 participants will be randomized in a CCI ratio to LY3526318 and placebo, respectively. It is expected that approximately 85% participants will complete the double-blind treatment period of the study. CCI

If there is no treatment difference between placebo and LY3526318, the probability of passing the efficacy criterion specified above (i.e., false positive) is less than 0.05. The simulation for the power calculation and sample size determination was carried out in FACTS Version 6.0.

10. Supporting Documentation and Operational Considerations

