5.2. Determination of Sample Size

Approximately 150 participants will be randomized in a CCI ratio to LY3526318 and placebo, respectively. It is expected that approximately 85% of participants will complete the double-blind treatment period of the study CCI

CCI

If there is no treatment difference between placebo and LY3526318, the probability of passing the efficacy criterion specified above (that is, false positive) is less than 0.05. The simulation for the power calculation and sample size determination was carried out in Fixed and Adaptive Clinical Trial Simulator (FACTS) version 6.0.

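### Protocol 9.1 puts the false-positive probability below 0.1, Protocol 9.5 and SAP 5.2 put it below 0.05, and nothing visible explains two levels

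*Protocol*

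**What the plan says.** Three places in the current text give the chance that an ineffective drug would meet the efficacy criterion.

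- Protocol 9.1 (Statistical Hypotheses): "the probability of passing the efficacy criterion specified above (i.e., false positive) is less than 0.1".
- Protocol 9.5 (Sample Size Determination): "the probability of passing the efficacy criterion specified above (i.e., false positive) is less than 0.05".
- SAP 5.2 (Determination of Sample Size): "the probability of passing the efficacy criterion specified above (that is, false positive) is less than 0.05".

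In each place the next sentence names the source of the work. Protocol 9.1: "The simulation for the power calculation and sample size determination was carried out using the Fixed and Adaptive Clinical Trial Simulator (FACTS) Version 6.0". Protocol 9.5: "The simulation for the power calculation and sample size determination was carried out in FACTS Version 6.0". SAP 5.2: "The simulation for the power calculation and sample size determination was carried out in Fixed and Adaptive Clinical Trial Simulator (FACTS) version 6.0".

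Protocol 9.5 and SAP 5.2 set the bound beside a planned size of about 150 participants. The definition of the criterion is redacted in all three sections, and so is the allocation ratio in Protocol 9.5 and SAP 5.2.

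**The concern.** The three sentences share the same null condition, refer to a single criterion and cite the same simulation, yet one prints a bound twice as large as the other two. Protocol 9.1 attributes its figure to the sample-size simulation, which is the subject of Protocol 9.5 and SAP 5.2, so it points to those sections and then disagrees with them.

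This is a proof-of-concept trial whose results are meant to guide further development. The design's operating characteristics come from simulation, and these sentences are the only visible numerical statement of false-positive control for the efficacy criterion. Someone who reads Protocol 9.1 learns that the risk of a false pass is under 1 in 10. Someone who reads Protocol 9.5 or the SAP learns that it is under 1 in 20. The visible text does not say which statement applies, or whether the two describe different criteria.

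**Working it through.** **Inputs**

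| Place | Stated bound | Stated source |
|---|---|---|
| Protocol 9.1 | < 0.1 | FACTS 6.0, power and sample-size simulation |
| Protocol 9.5 | < 0.05 | same |
| SAP 5.2 | < 0.05 | same |

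**Can either bound be reproduced?** No. The criterion, allocation ratio, effect size and standard deviation are redacted or not visible. The check is therefore a comparison of the printed figures.

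**Size of the mismatch.** Ratio: 0.1 / 0.05 = 2. Gap: 0.1 − 0.05 = 0.05, or 5 percentage points.

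**What the unknown rate would imply.** Let r be the simulated false-positive rate, and assume one common criterion.

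| r | Protocol 9.1 | Protocol 9.5 | SAP 5.2 | True statements |
|---|---|---|---|---|
| r < 0.05 | true | true | true | 3 of 3 |
| 0.05 ≤ r < 0.1 | true | false | false | 1 of 3 |
| r ≥ 0.1 | false | false | false | 0 of 3 |

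If Protocol 9.1 instead refers to a different criterion, both bounds can hold and only the labelling is missing.

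**Possible explanations, checked against the visible text**

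1. *Two criteria or two simulations.* No visible text announces a second one. The redacted text could.
2. *Multiplicity.* SAP 6.4 plans no formal adjustment, so no visible allocation of error produces two levels.
3. *Interim versus final.* SAP 6.15 plans interim analyses once 60% of participants have completed the four-week active period and leaves the details to a separate SAP. Protocol 9.4 gives no error level. Nothing visible ties either bound to an interim look.
4. *Sidedness.* A two-sided level of 0.10 and a one-sided level of 0.05 share the critical value 1.645, so a mix of conventions could produce this pair of numbers. None of the three sections mentions sidedness, however, and the probability of passing a given criterion under the null is a single number.
5. *A documented revision.* The SAP revision history lists no change to Section 5.2. The visible part of the protocol's change table lists none to 9.1 or 9.5.

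**The case against.** The strongest reply is that nothing here is a logical contradiction. Both figures are upper bounds, and any rate below 0.05 satisfies all three sentences. A ratio of two bounds is not a ratio of two error rates. This stands, and it is why the finding does not call either number false.

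The second reply is that the text each sentence points back to is redacted, and redacted text is not missing from the plan. The primary hypothesis is in the master protocol and the interim details are in a separate SAP, neither of which is available here. This also stands as a limit: a different criterion in Protocol 9.1 cannot be ruled out. It is not the natural reading, because Protocol 9.1 itself names the sample-size simulation. If there are two criteria, near-identical sentences without labels would still need to be told apart.

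Third, the two sections devoted to sample size agree on 0.05, so Protocol 9.1 may simply be a sentence that was never updated. That is plausible, but the documents do not show it. The simulated rate could also lie between the two bounds.

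Finally, nothing visible uses 0.1 or 0.05 as a decision threshold in the analysis. The visible models are Bayesian, and the figures are reported simulation properties. That is correct. It limits the consequence to how the design's false-positive control is described; it does not remove the mismatch in that description.

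**Conclusion.** The concern holds. The stated false-positive bound for the efficacy criterion is 0.1 in one place and 0.05 in two, a factor of two, with no visible explanation. This should be fixed, with medium confidence, because the criterion and the simulated rate cannot be seen.

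The conclusion rests on the printed sentences alone. What follows for each sentence depends on the unseen rate and on the assumption of a single criterion. Below 0.05, Protocol 9.1 is true but looser than it needs to be. From 0.05 up to but not including 0.1, Protocol 9.5 and SAP 5.2 are wrong. At 0.1 or more, all three are wrong. No effect on power or sample size is claimed.

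**What to change.** Look up the false-positive rate in the existing FACTS output for the criterion, sample size and allocation ratio of Protocol 9.5, and state the one matching figure in Protocol 9.1, Protocol 9.5 and SAP 5.2.

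- If the rate is below 0.05, tighten the statement in Protocol 9.1.
- If it is at least 0.05 but below 0.1, replace the statements in Protocol 9.5 and SAP 5.2.
- If it is 0.1 or more, replace all three.
- If Protocol 9.1 concerns a different criterion, label the two criteria and give each its own error rate.

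The cost is a look-up and a change to one to three sentences, with no added participants, procedures or simulations. If the rate is 0.05 or higher, the stated control becomes less favourable than Protocol 9.5 and SAP 5.2 now suggest.
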